#### 9.1.2.1.3 Antibodies against Botulinum Toxin

For analysis of antibodies against BoNT blood amounts appropriate in the context of all blood withdrawals during the study for the weight group of the subject will be taken ([Section 9.1.2.1](#)).

The serum amount necessary for FIA-AB is 1.5 mL and 4 mL for HDA. The estimated blood amount to yield the required serum amount is 4 mL for FIA-AB and 10 mL for HDA. For subjects  $\geq 21$  kg BW samples will be collected at the start of the study at Screening Visit and at the End of Study Visit (V17). For subjects  $< 21$  kg BW no blood samples for analysis of antibodies against BoNT will be taken to avoid an additional blood draw, if blood draw for the sample used for HDA testing would be only performed after a positive result of the FIA-AB test.

Sample work-up at the study site include preparation of serum by centrifugation at room temperature and transfer into provided tubes. Serum samples should preferably be stored at  $-20^{\circ}\text{C}$  ( $\pm 5^{\circ}\text{C}$ ) but must be within a range of  $-5^{\circ}\text{C}$  to  $-90^{\circ}\text{C}$  until frozen shipment to the analyzing laboratory.

Blood samples will be screened using the FIA-AB that detects antibodies against BoNT-A in human serum. FIA-AB detects binding to specific BoNT epitopes and allows the identification of sera that reacts with the toxin, but the FIA-AB is not capable to discriminate between neutralizing and non-neutralizing antibodies [[Göschel 1997](#)].

Samples that are positive in the FIA-AB will be tested using the validated mouse ex vivo HDA. The HDA is the most sensitive functional assay (sensitivity <0.5 mU/mL) currently available [Sesardic 2004]. To spare animals, the assay is performed only if the FIA-AB is positive.

#### 9.1.2.2 Specimen preparation, handling, storage, and shipping

Blood samples for clinical chemistry, hematology, and human chorionic gonadotropin will be tested by a central laboratory and will be handled according to the instructions of the central laboratory.

Blood samples intended for determination of antibodies against BoNT-A will be analyzed by [REDACTED] and [REDACTED]. Details of storage and coding as well as shipping procedures for these samples will be provided in a separate manual of operations.

No biological samples will be retained after this clinical study after the final clinical study report for this clinical study has been established.

## 9.2 Visit schedule

The purpose of the Screening Visit (V1) is to perform the check of a subject's eligibility for study participation. If all inclusion criteria and none of the exclusion criteria to be checked at Screening Visit (V1)/Baseline Injection Visit (V2, Day 1) are met (see Sections 7.2 and 7.3, the subject will be randomized to one of three dose groups of NT 201 by the IV/WRS. In subjects where both main clinical target patterns would qualify for injection, the main clinical target pattern for primary efficacy analysis will be randomized by an IV/WRS (for details see Section 8.2.1). After randomization, subjects will receive their 1st injection treatment with NT 201.

In OLEX three further treatments with NT 201 with the dosing regimen of the high dose group of MP will follow. After injections on the days of injection visits, the subject will be observed for a minimum of 30 minutes for immediate safety issues. The effect and safety of the treatment will be further observed until Week 12 to 16 (Week 14 ± 2 weeks) in each cycle of MP and OLEX.

Including Screening and Baseline Injection Visit, the subject and the parent(s) will come to the site for 14 visits and will have four telephone contacts. The number of visits may increase, if the Injection Visits of OLEX will be scheduled to revisits to a maximum of 17. To get additional information for scheduling reinjection at the end of MP, one additional optional telephone contact can be performed. Subjects (if applicable) and/or the parent(s) will be contacted by telephone at 7 days after injection treatments (TC1, TC2, TC3 and TC4 at Day 8 of the respective MP or OLEX treatment cycle).

If any Telephone Contact identifies an (S)AE/AESI that needs confirmation or treatment (e.g., respiratory disorder, dyspnoea, aspiration, dysphagia, speech disorder, dysphonia, other signs of bulbar palsy or botulism), the investigator will schedule a SV as soon as possible after the Telephone Contact. At 28 and 56 days after injection treatment of each cycle subjects will have Control Visits at the site (V3, V7, V11 and V15 at Day 29 and V4, V8, V12, and V16 at Day 57, respectively).

[figure not shown]
In case eligibility criteria for reinjection are not fulfilled at a scheduled visit (Final Visit of MP or End of Cycle Visits V9 and V13) at the end of an treatment cycle, the Injection Visit of the following treatment cycle can be postponed and rescheduled within up to 16 weeks after the previous injection treatment (for details see [Section 6.1](#))

[figure not shown]
Attempt should be made to arrange all visits at the same day time for an individual subject (i.e., morning or afternoon) to standardize treatment and assessment conditions. The End of Study Visit will be at Week  $14 \pm 2$  weeks (Day  $99 \pm 14$  days) of 4th treatment cycle. Study activities and visit schedule are detailed in [Table 16](#) and [Table 17](#).

[figure not shown]
---

 If the Final Visit of MP and the 1st Injection Visit of OLEX will be performed on the same day the results of these assessments can be transferred from V5 to V6.

**Table 16 Overview of Study Activities Main Period MP**

[figure not shown]

**Table 17 Overview of Study Activities in Open-Label Extension Period OLEX**

## 10 SAFETY ASSESSMENTS

### 10.1 Definition of an adverse event

An AE is any untoward medical occurrence in a subject administered a pharmaceutical product that does not necessarily have a causal relationship with the treatment. Thus, an AE can be any unfavorable and unintended sign, symptom, or disease (including intercurrent illness); deterioration of a pre-existing illness; accident; any suspected drug reaction; or a clinically relevant change of laboratory values whether or not considered related to the IP and/or study treatment.

Changes in efficacy variables (e.g., investigator, subject- and/or parent-reported outcome variables during the course of the study) are not intended to be documented as AEs, because these changes will be recorded as efficacy variables. Elective treatments planned before screening and which are documented in the subject's source data are usually not regarded as AEs. Pre-existing conditions that do not worsen during the course of the study are not reportable as AEs. Abnormal clinical relevant laboratory values obtained during the screening period will only meet AE criteria if newly detected. However, if laboratory values resulting from pre-existing conditions worsen to clinical relevance during the course of the study AE criteria are met.

The period of observation for an AE extends from the time when the IC form was signed until the End of Study Visit, i.e., 12 to 16 weeks after last administration of IP in OLEX. Any medical occurrence that happens between the time when the IC form is signed and the 1st intake of IP is an AE and has to be documented in the subject's file and in the eCRF AE report form. Any ongoing AEs will not be followed up after the End of Study Visit, which is scheduled up to 16 weeks after last injection of IP in OLEX.

Data pertaining to AEs will be collected during each study visit based on the subject's (if applicable) or parent(s)'s spontaneous description, through investigator inquiry, or discovered in the course of examinations done during the visit. The investigator will assess and record any AE in detail in the subject's file and on the eCRF AE report form. The following information must be recorded:

- AE diagnosis or main symptom.
- Date of onset.
- Date of worsening.
- Intensity (maximum observed; see [Section 10.1.1](#)).
- Causal relationship (not related, related, see [Section 10.1.2](#)).
- Serious (yes or no, see [Section 10.2](#)).

- Outcome (see [Section 10.1.3](#)).
- Action taken with IP(s) (see [Section 10.1.3](#)).
- AE leading to discontinuation of the study (yes or no).
- Stop date.

After completion of all scheduled visit assessments the investigator must document any AEs arising from these assessments.

In case of an SAE, or AESI (alert term, as defined in [Section 10.3](#)), the investigator must also complete an SAE report form or AESI report form and report it to the CRO within 24 hours, as described in [Section 10.2](#) and [10.3](#).

Treatment of overdose with IP is described in [Section 8.2.6](#).

### **10.1.1 Definition of intensity**

The clinical intensity of an AE will be classified as:

*Mild:* Signs and symptoms that can be easily tolerated. Symptoms can be ignored and disappear when the subject is distracted.

*Moderate:* Signs and symptoms that cause discomfort and interfere with normal functioning, but are tolerable. They cannot be ignored and do not disappear when the subject is distracted.

*Severe:* Signs and symptoms that affect usual daily activity and incapacitate the subject, thereby interrupting the daily activities.

The definitions above are difficult to apply for some data (e.g., clinically relevant laboratory values that are documented and evaluated on the eCRF AE report form). In such situations, the investigator should make a judgment based on personal experience.

### **10.1.2 Definition of causal relationship with investigational product(s)**

An AE is considered to be ‘related’ to IP if a causal relationship between the IP and an AE is at least a reasonable possibility (i.e., the relationship cannot be ruled out).

The expression ‘reasonable causal relationship’ is meant to convey that there are facts (evidence) or arguments to suggest a causal relationship (ICH E2A guideline). Otherwise, the relationship should be considered as ‘not related’.

### **10.1.3 Categories of actions taken and outcome**

Action(s) taken with IP:

- Drug withdrawn.
- Dose reduced.
- Dose increased.
- Dose not changed.
- Unknown.
- Not applicable.
- Drug withdrawn temporarily

The reportable outcomes and/or sequelae of an AE are as follows:

- Recovered/resolved.
- Recovering/resolving.
- Not recovered/not resolved.
- Recovered/resolved with sequelae.
- Fatal.
- Unknown.

### **10.2 Definition of a serious adverse event**

An SAE is any untoward medical occurrence, at any dose, that:

- Results in death.
- Is life-threatening.
- Requires inpatient hospitalization, or prolongation of existing hospitalization.

---

 If there is more than 1 AE, only the AE leading to death will be attributed with a 'fatal' outcome.

 The term 'life-threatening' in the definition of 'serious' refers to an event in which the child/adolescent was at risk of death at the time of the event; it does not refer to an event that hypothetically might have caused death if it were more severe.

- Results in persistent or significant disability/incapacity.
- Is a congenital anomaly/birth defect.
- Consists of any other medically important condition.

In case of death, an autopsy report should be submitted (if available). The date and cause of death should be recorded.

Hospitalizations for elective treatments planned before screening and which are documented in the subject's source data are usually not regarded as SAEs. Hospitalizations for analgo-sedation starting one day before or on the day of injection treatment (V2 and V7) for organizational reasons only (e.g. to allow for an early start of the Injection Visits in the morning in subjects living far from the site) are generally not regarded as SAEs. However, if any event during or after analgo-sedation would trigger an overnight stay, this will qualify as SAE. The same applies, if analgo-sedation was started in an outpatient setting at the site and then has been changed to an inpatient setting, e.g. due to an unexpectedly long monitoring phase post intervention.

All SAEs that occur during the study period, whether considered to be related to IP or not, must be reported by telefax, telephone or e-mail within 24 hours of knowledge of the event. SAE report forms are provided in the ISF.

Although all information required for completion of an SAE report form may not be available within the specified time period, an initial report should be submitted if the following minimal information is available:

- An identifiable subject (number, initials).
- A suspect product.
- An identifiable reporting source (investigator/study site identification).
- An event or outcome that can be identified as serious.

The report must be delivered to the individual(s) listed below.

[REDACTED]

[REDACTED]

---

 According to ICH E2A, CPMP/ICH/377/95: 'Medical and scientific judgment should be exercised in deciding whether expedited reporting is appropriate in other situations, such as important medical events that may not be immediately life-threatening or result in death or hospitalization but may jeopardize the patient/subject or may require intervention to prevent one of the other outcomes listed in the definition above. These should also usually be considered serious. Examples of such events are intensive treatment in an emergency room or at home for allergic bronchospasm; blood dyscrasias or convulsions that do not result in hospitalization; or development of drug dependency or drug abuse.'

If SAE fax fails, use email as back-up for all regions:

Email: [REDACTED]

If the report is sent via email then the completed and signed fax form must be attached to the email. A simple notification email of the event is not sufficient. The CRO will transmit all SAE reports within 1 business day to Merz drug safety.

The investigator, Merz Pharmaceuticals GmbH, and the CRO will comply with the applicable regulatory requirements related to the reporting of suspected unexpected serious adverse reactions [SUSAR]s to the regulatory authorities and the IEC(s)/IRB(s).

Furthermore the investigator has to report the SAE to the responsible IEC/IRB according to local requirements.

The investigator must supply further supporting information within 3 days of knowledge of the SAE, and a detailed SAE description is an integral part of this supporting information. Follow-up reports should be sent without delay to the drug safety department at the CRO as an SAE report form (marked as a 'follow-up' report) and accompanied by appropriate supporting documentation (e.g., hospital reports). The SAE has to be followed up until a final outcome and date are available. These SAEs will be followed-up only in the Global Drug Safety database after final SAE reconciliation is completed.

All SAEs will be reviewed by the DMC. Details will be described in a DMC charter.

SAEs occurring after the end of the observational period need only be reported if the investigator considers the event to be related to IP. These reports generally will not be entered into the study database.

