### **Main Period (MP):**

Baseline Injection Visit (V2): Day 1, randomization

Telephone Contact (TC1): Day 8 (Week 1)  $\pm$  3 days of MP

Ctrl. Visit (V3): Day 29 (Week 4)  $\pm$  3 days of MP

Ctrl. Visit (V4): Day 57 (Week 8)  $\pm$  3 days of MP

Optional Telephone Contact  
Wk12: Day 85 (Week 12)  $\pm$  3 days of MP

Final Visit of MP (V5) Day 99 (Week 14)  $\pm$  14 days of MP

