### **Open-Label Extension Period (OLEX)**

Injection Visit (V6, V10, V14): Day 1 of the 2nd to 4th treatment cycle.

Telephone Contact  
(TC2, TC3, TC4): Day 8 (Week 1)  $\pm$  3 days of 2nd to 4th treatment cycle.

Ctrl. Visit (V7, V11, V15): Day 29 (Week 4)  $\pm$  3 days of 2nd to 4th treatment cycle

Ctrl. Visit (V8, V12, V16): Day 57 (Week 8)  $\pm$  3 days of 2nd to 4th treatment cycle

End of Cycle Visit (V9, V13) Day 99 (Week 14)  $\pm$  14 days of 2nd and 3rd treatment cycle

End of Study Visit (V17): Day 99 (Week 14)  $\pm$  14 days of 4th treatment cycle.

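### The SAE exemption for organisational overnight stays names V7, a control visit without injection, and leaves out the re-injection visits V6, V10 and V14

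*Protocol*

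**What the plan says.** Protocol section 10.2 lists inpatient hospitalisation among the criteria that make an untoward medical occurrence serious. It then sets out an exception: hospital stays for analgosedation that begin one day before or "on the day of injection treatment (V2 and V7) for organizational reasons only" "are generally not regarded as SAEs". The example given is a stay "to allow for an early start of the Injection Visits in the morning in subjects living far from the site". The same paragraph keeps two situations as SAEs: an event during or after analgosedation that leads to an overnight stay, and a switch from an outpatient to an inpatient setting, for instance because monitoring takes unexpectedly long.

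The visit schedule in Protocol section 6.1, repeated in the synopsis and in SAP section 3.1, gives the main-period (MP) injection as "Baseline Injection Visit (V2): Day 1, randomization". For the open-label extension (OLEX) it lists "Injection Visit (V6, V10, V14): Day 1 of the" each cycle and, separately, "Ctrl. Visit (V7, V11, V15): Day 29 (Week 4"). Protocol section 9.2 agrees, placing "V3, V7, V11 and V15 at Day 29". Protocol section 8.3.1 allows analgosedation on injection days in both MP and OLEX.

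**The concern.** The exemption contains one list of visits, and that list contradicts the schedule. A site or monitor who checks an overnight stay at V6, V10 or V14 against section 10.2 does not find the visit there. The same event-free stay may then be left unreported at V2 and reported as an SAE at a later injection, or be handled differently from site to site.

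Once a stay is classed as an SAE, section 10.2 requires a report within 24 hours, supporting information within 3 days, transmission to the sponsor's drug safety function, a report to the IEC/IRB where local rules ask for it, and DMC review. It also enters planned outputs. SAP section 6.5.2 tabulates serious TEAEs for MP, and for OLEX overall and per cycle. SAP section 7.7.5 breaks serious TEAEs down by use of local anaesthesia or analgosedation. Entries with no medical event behind them would add noise to those tables and could be mistaken for a signal linked to sedation.

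**Working it through.** There is no stated figure to reproduce. The check compares the list with the schedule and then follows where a reported stay would be counted.

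**Step 1. List against schedule** (Protocol sections 6.1, 9.1.2.1.2 and 9.2; SAP section 3.1)

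| Visit | Role in the schedule | Named in the exemption |
|---|---|---|
| V2 | Injection, MP | Yes |
| V6 | Injection, cycle 2 | No |
| V7 | Control visit, Week 4 of cycle 2, no injection | Yes |
| V10 | Injection, cycle 3 | No |
| V14 | Injection, cycle 4 | No |

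There are 4 injection visits. The list has 2 entries, of which 1 (V2) is an injection visit. Injection visits not named: 4 − 1 = 3. The V7 entry is empty in effect, because the exemption is tied to an injection and none is given at V7.

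**Step 2. What the whole sentence supports.** Two readings are open.
- If the list is taken as complete, the exemption reaches V2 only and misses three of four sessions.
- If the list is taken as a faulty illustration, the references to injection treatment and to injection visits in the plural cover all four.

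The text does not settle which reading applies, and the two give different answers for the same stay.

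**Step 3. Where a reported stay would be counted.** Protocol section 12.4.5 and SAP section 7.5.2 close the MP window at the time of the V6 injection. The SAP assigns an OLEX event to the cycle of the most recent injection. Taking the start of the stay as the onset:

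| Session | Stay begins before the injection | Onset at or after the injection |
|---|---|---|
| V2 | Not treatment-emergent; listed only | MP |
| V6 | MP | Cycle 2 |
| V10 | Cycle 2 | Cycle 3 |
| V14 | Cycle 3 | Cycle 4 |

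A travel stay that begins the evening before V6 would therefore go to the MP table, not to OLEX. If all three unnamed sessions had such stays, OLEX would gain two entries and MP one.

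**Step 4. Analgosedation subgroup.** SAP section 7.7.5 defines this subgroup by use at the corresponding injection. Stays with onset at or after an injection would all fall among sedated sessions. A stay that begins before the injection is assigned to the preceding cycle, so its subgroup depends on whether sedation was used at that earlier injection.

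**Step 5. Size.** A subject who completes the study has 3 unnamed sessions, so the number of administrative entries per subject lies between 0 and 3. The documents give no frequency of overnight stays and no information on how sites read the rule, so the position within that range cannot be estimated.

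**The case against.** The strongest reply is that this is only a slip in a visit number. The operative words concern injection treatment, the stated purpose refers to injection visits in general, and the exemption is qualified as a general rule. An SAE also requires an untoward medical occurrence, and a stay arranged only for travel is not one. On this view a sensible site would apply the exemption at every injection visit. In addition, the safety analysis is descriptive, no test of MP against OLEX is planned, and DMC physicians would recognise an event-free stay.

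Most of this stands, and it rules out two stronger readings that a reader might infer.

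- **That organisational stays at V6, V10 and V14 count as SAEs.** No passage says so. The inference needs the list to override the rest of its own sentence and the definition of an SAE.
- **That OLEX serious-TEAE rates are inflated by a calculable amount, such as three times a per-session stay rate.** No stay rate is given. The multiplier of three assumes that every subject has all three OLEX injections and that every site takes the list literally. Stays that begin before the V6 injection would also be counted in MP.

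The reply does not remove the contradiction. If the definition of an SAE settled every case, the exemption sentence would not be needed. The same paragraph classes some sedation-related stays as SAEs, so sites do have to draw this line and need a correct list to do it.

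**Conclusion.** Wrong as written, low severity. Section 10.2 contradicts the visit schedule: it names a visit with no injection and leaves out three of the four injection visits. The supportable consequence is inconsistent classification of identical organisational stays. This can add administrative entries to expedited reporting, DMC review and the descriptive serious-TEAE counts per cycle and by analgosedation use.

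The size cannot be derived from the documents. It depends on how often such stays occur and how many sites take the list as complete. Efficacy analyses are unaffected. The rule is the same for all dose groups, V2 is named correctly, and nothing suggests that organisational stays differ by dose. No bias between dose groups is therefore expected, even though a stay just before V6 would be counted in MP.

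**What to change.** Reconcile the parenthesis in section 10.2 with the protocol's own schedule so that it names all injection visits (V2, V6, V10 and V14). Send a short notice to sites and drug safety. Leave unchanged the rule that an event during or after analgosedation which triggers an overnight stay is an SAE. If stays at V6, V10 or V14 have already been reported as SAEs, identify them and review their classification before database close.

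The cost is a one-line protocol correction and the notice. No SAP text, analysis or sample size changes.

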### **10.3 Adverse events of special interest (alert terms)**

AEs occurring after treatment that are thought to possibly indicate toxin spread are defined as AESIs (see [Table 18](#)). The subject (if applicable) and parent(s) will be actively asked by the investigator or an authorized delegate at each visit starting at V2 as well as during the telephone contact (starting at TC1 in MP) if any of the AESI occurred since the last contact. The questioning and documentation of answers will be standardized. AESI questioning at V2 will facilitate recording of pre-existing conditions and/or possibly undetected (S)AEs that could confound AESI questioning post injection of IP.

The site must report all AESIs that occur during the study period, whether considered to be related to IP or not, by telefax to the responsible CRO within 24 hrs of knowledge of the event. The CRO will transmit these AESIs to Merz Pharmaceuticals GmbH. Each

AESI must be reported by the site on the AESI reporting form. Moreover, AESIs should be reported on the general pages of the eCRF as well as in the subject's file. The AE form in the eCRF as well as the eCRF pages for Medical History/Concomitant Diseases and for Previous/Concomitant Medication and Non-Drug Treatment shall be faxed/sent along with the AESI reporting form.

